#### **4.2.1.3.1 Dose Adjustments for Hematologic Toxicities during Multiple Myeloma Treatment**

Dose modification guidelines, as summarized below in [Table 4](#) and [Table 5](#), are recommended to manage Grade 3 or 4 neutropenia or thrombocytopenia or other Grade 3 or 4 toxicities judged to be related to lenalidomide. Please refer to local product label for additional guidelines.

**Table 4 Platelet Counts: Thrombocytopenia in MM**

When Platelets	Recommended Course
Fall to <30,000/mcL  Return to $\geq 30,000/\text{mcL}$	Interrupt lenalidomide treatment, follow CBC weekly  Restart lenalidomide at 15 mg daily
For each subsequent drop <30,000/mcL Return to $\geq 30,000/\text{mcL}$	Interrupt lenalidomide treatment  Resume lenalidomide at 5 mg less than the previous dose. Do not dose below 5 mg daily.

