## 1.0 TRIAL DESIGN

### 1.1 Trial Design

This is an open-label, Phase II, single center trial of pembrolizumab (MK-3475), lenalidomide and dexamethasone in subjects with high risk Multiple Myeloma (hrMM) post high-dose chemotherapy with autologous stem cell transplantation (ASCT).

Pembrolizumab (MK-3475), [name], HUMC

Patients with high-risk MM defined as those with one of the following abnormalities who have undergone induction therapy followed by single or tandem melphalan -based ASCT will be considered eligible.

1. International Staging System (ISS) stage 3 (See Appendix 3 for ISS Staging) and/or
2. Deletion 13q by cytogenetics and/or
3. 1q amplification, 1p deletion, p53 deletions (17p deletions), t(4;14), t(14;16), t(14;20), hypodiploidy by FISH and/or
4. High-risk gene expression profile (GEP) scores

Post engraftment, between days +60 and day +180 post ASCT patients will undergo restaging evaluation to include a screening BM aspirate and biopsy. Patients will then be initiated on pembrolizumab, lenalidomide and dexamethasone for 2 cycles followed by pembrolizumab and lenalidomide alone for 2 cycles for a total period of 4 months.

Adverse events will be monitored at every visit and graded in severity according to the guidelines outlined in the NCI Common Terminology Criteria for Adverse Events (CTCAE) version 4.03. (See Appendix 1).

Treatment with pembrolizumab, lenalidomide and dexamethasone for the first 2 cycles then pembrolizumab and lenalidomide will continue for cycle 3 and 4 for a total of four cycles or until unacceptable adverse event(s), documented confirmed disease progression, intercurrent illness that prevents further administration of treatment, investigator's decision to withdraw the subject, subject withdraws consent, pregnancy of the subject, noncompliance with trial treatment or procedure requirements, or administrative reasons. After the completion of cycle 4, each subject will be followed for 30 days for adverse event monitoring (serious adverse events will be collected for 90 days after the end of treatment). Subjects who discontinue treatment for reasons other than disease progression will have post-treatment follow-up for disease status until disease progression, initiating a non-study cancer treatment, withdrawing consent, or becoming lost to follow-up. All subjects will be followed by telephone contact for overall survival until death, withdrawal of consent or the end of the trial, whichever comes first.

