#### 4.2.1.3 Dose Modification Guidelines for Lenalidomide

Dose modification guidelines are based on the recommendation provided by the Myeloma expert panel review[58] of the efficacy and toxicity of lenalidomide plus dexamethasone, and the guidance provided in the product label for lenalidomide. Any toxicity associated with lenalidomide that prompts a dose reduction of lenalidomide is outlined in the Sections below.

Lenalidomide is administered once daily from Day 1 through Day 14 in each 21 day cycle. If a subject receiving 5 mg of lenalidomide experiences an AE related to lenalidomide and is in need of dose modification, the subject should discontinue lenalidomide and continue only pembrolizumab (MK-3475) and dexamethasone, as 5 mg is the lowest dose used in

Pembrolizumab (MK-3475), [name], HUMC

this trial. A maximum of three dose reductions of lenalidomide will be allowed in the order indicated in Table 6, where applicable. The duration of administration will remain the same.

A subject cannot be restarted on lenalidomide unless non-hematologic lenalidomide-related toxicities have returned to at least Grade 1 toxicity or baseline.

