**Table 5 Absolute Neutrophil Counts (ANC): Neutropenia in MM**

When Neutrophils	Recommended Course
Fall to <1,000/mcL  Return to $\geq 1,000/\text{mcL}$ and neutropenia is the only toxicity	Interrupt lenalidomide treatment, add G-CSF, follow CBC weekly  Resume lenalidomide at 25 mg daily
Return to $\geq 1,000/\text{mcL}$ and if other toxicity	Resume lenalidomide at 15 mg daily

For each subsequent drop $<1,000/\text{mcL}$	Interrupt lenalidomide treatment
Return to $\geq 1,000/\text{mcL}$	Resume lenalidomide at 5 mg less than the previous dose. Do not dose below 5 mg daily.
 If the subject is receiving Len 10 mg, the subject may resume Len at 5 mg.	

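### Table 4 restarts lenalidomide at a fixed 15 mg after a first platelet fall, so read literally it raises a patient already reduced to 10 mg and gives a 15 mg patient no reduction

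*Combined protocol and SAP*

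**What the plan says.** Lenalidomide starts at 25 mg on Days 1 to 14 of each 21-day cycle (section 4.2), "for a total of four cycles" (section 1.1). Section 4.2.1.3 permits stepwise reduction: "A maximum of three dose reductions of lenalidomide will be allowed in the order indicated in Table 6, where applicable". Table 6 lists the levels as 25, 15, 10 and 5 mg. A patient on 5 mg who needs a further change for a lenalidomide-related event stops the drug.

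For cytopenias, Tables 4 and 5 "are recommended to manage Grade 3 or 4 neutropenia or thrombocytopenia", followed by "Please refer to local product label for additional guidelines".

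- **Table 4, first platelet fall below 30,000/mcL:** "Restart lenalidomide at 15 mg daily" on recovery. Later falls take 5 mg off the previous dose.
- **Table 5, first ANC fall below 1,000/mcL:** on recovery "and neutropenia is the only toxicity", the entry is "Resume lenalidomide at 25 mg daily". If there is other toxicity, the restart is 15 mg. For later falls: "Resume lenalidomide at 5 mg less than the previous dose".
- **Footnotes:** Tables 5 and 6 each allow a patient on 10 mg to resume at 5 mg. Table 4 has no such footnote.

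**The concern.** The first-fall entries are fixed doses that fit a patient still on 25 mg. The remaining restart rules (later falls in Tables 4 and 5, and Table 6) are relative to the dose in use. A patient who has already been stepped down for other toxicities and then has a first platelet fall is sent by Table 4 to a dose that takes no account of those reductions. At 10 mg the printed recommendation is an increase, back to a level already abandoned for toxicity, immediately after a new toxicity. At 15 mg it is no change. What is at stake is the safety of a few heavily affected patients, and consistent dosing from one treating physician to the next.

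**Working it through.** The plan states no figure on this point, so there is none to reproduce. The check applies the tables as written.

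**Step 1. Can a patient be on 15 or 10 mg before any platelet fall?** Let P be a platelet fall, N an isolated ANC fall, NO an ANC fall with other toxicity, and O another Grade 3/4 toxicity handled by Table 6. One event (O or NO) takes 25 mg to 15 mg. Four two-event orders reach 10 mg, and P then follows as the third event:

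- O, O, P: 25, 15, 10, then 15 mg
- NO, O, P: 25, 15, 10, then 15 mg
- NO, N, P: 25, 15, 10 (later-fall row), then 15 mg
- NO, NO, P: 25, 15, 10 (later-fall row), then 15 mg

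So the raise needs at least three events and the no-reduction restart at least two (O, P or NO, P). None of these orders depends on how Table 5's sole-toxicity condition is read.

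**Step 2. First-fall restart by dose at interruption, read literally.**

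| Dose held (mg) | Table 4 | Table 5, isolated | Table 5, other toxicity |
|---|---|---|---|
| 25 | 15 (-10) | 25 (0) | 15 (-10) |
| 20 | 15 (-5) | does not arise | does not arise |
| 15 | 15 (0) | 25 (+10), if this row applies | 15 (0) |
| 10 | 15 (+5) | 25, but footnote permits 5 | 15, but footnote permits 5 |
| 5 | 4.2.1.3: discontinue | 4.2.1.3: discontinue | 4.2.1.3: discontinue |

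A dose of 20 mg arises only from 25 - 5 after a second ANC fall, so Table 5's first-fall rows cannot apply there.

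**Step 3. Table 5 at 15 mg.** If the sole-toxicity condition refers to the current episode, a 15 mg patient with a first isolated ANC fall goes to 25 mg (orders P, N or O, N). If an earlier, resolved toxicity counts, the other-toxicity row applies and the dose stays at 15 mg. The table does not say which is meant.

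**Step 4. Size.** Dose per 14-day course:

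- 14 x 10 = 140 mg and 14 x 15 = 210 mg. The raise is 70 mg; 210/140 = 1.50, or +50%.
- Table 5 at 15 mg, on the first reading: 14 x 25 = 350 mg. The raise is 140 mg; 350/210 = 1.67, or +67%. On the other reading it is zero.

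All events must fall within 4 x 14 = 56 scheduled lenalidomide days and the gaps between them.

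**The case against.** The best answer is that no raise is intended. Section 4.2.1.3 governs all three tables and sets reductions in the order 25, 15, 10, 5 mg. On that view 15 mg in Table 4 is simply the first step down from the starting dose, as section 4.2 also suggests. The tables are recommendations and point to the product label, so a physician would be unlikely to increase a dose after thrombocytopenia. Other rules also thin out the paths: section 4.8 removes patients with unacceptable adverse events, and the note to Table 3a permanently stops treatment for a recurrent Grade 3 drug-related event or a life-threatening one, though that is a pembrolizumab rule.

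Most of this stands as evidence of intent and of low frequency. It does not close the gap. The ordering sentence limits reductions, is qualified by its closing words, and sets no ceiling on a restart. The label is cited for additional guidance, and its content is not in the documents. Advisory status lets a physician depart from the entry but does not make the entry right.

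A reader might go further and infer that both tables are silent for everyone below 25 mg. They are not: Table 5's footnote addresses 10 mg, though only permissively, and section 4.2.1.3 settles 5 mg. Nor can one say that Table 5 definitely raises a 15 mg patient to 25 mg, since that depends on an unstated meaning.

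**Conclusion.** The point holds for Table 4: its first-fall entry, taken literally, raises a 10 mg patient by 50% and gives a 15 mg patient no reduction, and nothing else in the protocol caps the restart. Table 5 contributes an ambiguity at 15 mg only.

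This is a minor, infrequent dosing-safety correction. It would be wrong to infer that the protocol means to escalate, that many patients are exposed, or that the results are affected. Section 4.2.1.3 points away from the first. The documents give no event rates to support the second. The endpoint, power and efficacy analysis do not depend on these entries.

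The conclusion assumes that Table 4 is complete as it appears in the protocol text, with no footnote, and that the label supplies no overriding rule, which cannot be checked here.

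**What to change.** 1. In 4.2.1.3, state that a lenalidomide restart dose never exceeds the dose held at interruption.
2. In Table 4, first-fall row: *15 mg daily or, if already at 15 mg or lower, 5 mg less than the dose at interruption (15 to 10, 10 to 5; at 5 mg discontinue per 4.2.1.3).*
3. In Table 5, isolated neutropenia: replace 25 mg with *the dose at interruption*.
4. In Table 5, other toxicity: use the same 15-mg-or-lower rule as in item 2.

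A cap alone would stop the raise but would still restart 15 and 10 mg patients unreduced after platelets below 30,000/mcL, which is out of step with Table 4's later-fall row and Table 6. Item 2 matches both.

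Result for doses held of 25, 15 and 10 mg: Table 4 gives 15, 10 and 5; Table 5 isolated gives 25, 15 and 10 (the footnote still permits 5 at 10 mg); Table 5 with other toxicity gives 15, 10 and 5. A 20 mg patient still goes to 15 mg under Table 4. No dose rises, and the rules at 25 mg are unchanged. Saying in Table 5 whether the sole-toxicity condition means the current episode would also settle which row applies.

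The cost is one sentence and three table entries, with no change to sample size or analysis.

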**Table 5 Absolute Neutrophil Counts (ANC): Neutropenia in MM**

When Neutrophils	Recommended Course
Fall to <1,000/mcL  Return to $\geq 1,000/\text{mcL}$ and neutropenia is the only toxicity	Interrupt lenalidomide treatment, add G-CSF, follow CBC weekly  Resume lenalidomide at 25 mg daily
Return to $\geq 1,000/\text{mcL}$ and if other toxicity	Resume lenalidomide at 15 mg daily

For each subsequent drop $<1,000/\text{mcL}$	Interrupt lenalidomide treatment
Return to $\geq 1,000/\text{mcL}$	Resume lenalidomide at 5 mg less than the previous dose. Do not dose below 5 mg daily.
 If the subject is receiving Len 10 mg, the subject may resume Len at 5 mg.	

#### 4.2.1.3.2 Other Grade 3/4 Toxicities in MM

For other Grade 3/4 toxicities, hold treatment and restart at the physician's discretion at next lower dose level when toxicity has resolved to  $\leq$  Grade 2 as outlined below in [Table 6](#).

Table 6 Lenalidomide Dose Reductions for Subjects with Other Grade 3/4 Toxicities

Modification	Dose 
Starting Dose	Lenalidomide 25 mg every day for 14 days, every 21 days
Dose Reduction 1	Lenalidomide 15 mg every day for 14 days, every 21 days
Dose Reduction 2	Lenalidomide 10 mg every day for 14 days, every 21 days
Dose Reduction 3	Lenalidomide 5 mg every day for 14 days, every 21 days
 Do not dose below 5 mg daily	
 If the subject is receiving Len 10 mg, the subject may resume Len at 5 mg.	

#### 4.2.1.3.3 Recommended Dose Adjustments for Subjects with Impaired Renal Function

Renal function may be impaired in subjects with MM by immunoglobulin light chains, amyloidosis. MM subjects with normal renal function may develop renal dysfunction or renal impairment during treatment with lenalidomide and dexamethasone. If renal toxicity occurs during study treatment, drug should not be restarted unless the toxicity resolved to  $\leq$  Grade 1.

#### 4.2.1.4 Dose Modification Guidelines for Dexamethasone

Dexamethasone will be given at 40 mg q.d. p.o. on Days 1, 8, and 15 (i.e. once weekly) in each 21-day cycle. If a subject experiences adverse events, up to two dose reductions of dexamethasone will be allowed. The duration of administration will remain the same; however, the daily dose will be modified. For grade 3 or 4 toxicities, the dose will be modified from a starting dose of 40 mg to 20 mg, and a second dose reduction can be to 10 mg. For grade 3 or 4 toxicities in patients >75, in the starting dose of 20 mg can be dose reduced to 10 mg and then a second dose reduction can be to 4 mg. Additional supportive care guidelines specific to dexamethasone are indicated in [Table 7](#).

A subject cannot be restarted on dexamethasone unless non-hematologic dexamethasone related toxicities have returned to at least Grade 1 toxicity or baseline.

#### 4.2.1.4.1 Supportive Care Guidelines Specific to Dexamethasone

Table 7 Supportive Care Guidelines Specific to Dexamethasone

Body System	Symptom	Recommended Action
Gastrointestinal	Dyspepsia, gastric or duodenal ulcer, gastritis Grade 1–2 (requiring medical management)	Treat with H2 blockers, sucralfate, or omeprazole. If symptoms persist despite above measures, decrease dexamethasone dose by one dose level.
Gastrointestinal	> Grade 3 (requiring hospitalization or surgery)	Hold dexamethasone until symptoms adequately controlled. Restart and decrease one dose level of current dose along with concurrent therapy with H2 blockers, sucralfate, or omeprazole. If symptoms persist despite above measures, discontinue dexamethasone and do not resume.
Gastrointestinal	Acute pancreatitis	Discontinue dexamethasone and do not resume.
Cardiovascular	Edema >Grade 3 (limiting function and unresponsive to therapy or anasarca)	Diuretics as needed, and decrease dexamethasone dose by one dose level; if edema persists despite above measures, decrease dose another dose level. Discontinue dexamethasone and do not resume if symptoms persist despite second reduction.
Neurology	Confusion or Mood alteration > Grade 2 (interfering with function +/- interfering with activities of daily living)	Hold dexamethasone until symptoms resolve. Restart with one dose level reduction. If symptoms persist despite above measures, discontinue dexamethasone do not resume.
Musculoskeletal	Muscle weakness > Grade 2 (symptomatic and interfering with function +/- interfering with activities of daily living)	Decrease dexamethasone dose by one dose level. If weakness persists despite above measures, decrease dose by one dose level. Discontinue dexamethasone and do not resume if symptoms persist.

Metabolic	Hyperglycemia > Grade 3 or higher	Treatment with insulin or oral hypoglycemics as needed. If uncontrolled despite above measures, decrease dose by one dose level until levels are satisfactory.
-----------	-----------------------------------	--

#### 4.2.2 Timing of Dose Administration

Trial treatment should be administered on Day 1 of each cycle after all procedures/assessments have been completed as detailed on the Trial Flow Chart (Section 5.0). Trial treatment may be administered up to 3 days before or after the scheduled Day 1 of each cycle due to administrative reasons.

All trial treatments will be administered on an outpatient basis.

Pembrolizumab 200 mg will be administered as a 30 minute IV infusion every 3 weeks. Sites should make every effort to target infusion timing to be as close to 30 minutes as possible. However, given the variability of infusion pumps from site to site, a window of -5 minutes and +10 minutes is permitted (i.e., infusion time is 30 minutes: -5 min/+10 min).

#### 4.2.3 Trial Blinding/Masking

This is an open-label trial; therefore, the Sponsor, investigator and subject will know the treatment administered.

### 4.3 Randomization or Treatment Allocation

No randomization or treatment allocation will be used in this trial as it is a single arm, open-label trial.

### 4.4 Stratification

No stratification based on age, sex or other characteristic will be used in this trial.

### 4.5 Concomitant Medications/Vaccinations (allowed & prohibited)

Medications or vaccinations specifically prohibited in the exclusion criteria are not allowed during the ongoing trial. If there is a clinical indication for one of these or other medications or vaccinations specifically prohibited during the trial, discontinuation from trial therapy or

vaccination may be required. The final decision on any supportive therapy or vaccination rests with the investigator and/or the subject's primary physician.

#### **4.5.1 Acceptable Concomitant Medications**

All treatments that the investigator considers necessary for a subject's welfare may be administered at the discretion of the investigator in keeping with the community standards of medical care. All concomitant medication will be recorded on the case report form (CRF) including all prescription, over-the-counter (OTC), herbal supplements, and IV medications and fluids. If changes occur during the trial period, documentation of drug dosage, frequency, route, and date may also be included on the CRF.

All concomitant medications received within 28 days before the first dose of trial treatment and 30 days after the last dose of trial treatment should be recorded. Concomitant medications administered after 30 days after the last dose of trial treatment should be recorded for SAEs.

#### **4.5.2 Prohibited Concomitant Medications**

Subjects are prohibited from receiving the following therapies during the Screening and Treatment Phase (including retreatment for post-complete response relapse) of this trial:

- Antineoplastic systemic chemotherapy or biological therapy
- Immunotherapy not specified in this protocol
- Chemotherapy not specified in this protocol
- Investigational agents other than pembrolizumab
- Radiation therapy
  - Note: Radiation therapy to a symptomatic solitary lesion or to the brain may be allowed at the investigator's discretion.
- Live vaccines within 30 days prior to the first dose of trial treatment and while participating in the trial. Examples of live vaccines include, but are not limited to, the following: measles, mumps, rubella, varicella/zoster, yellow fever, rabies, BCG, and typhoid vaccine.
- Systemic glucocorticoids for any purpose other than to modulate symptoms from an event of clinical interest of suspected immunologic etiology. The use of physiologic doses of corticosteroids may be approved after consultation with the Sponsor.

Subjects who, in the assessment by the investigator, require the use of any of the aforementioned treatments for clinical management should be removed from the trial. Subjects may receive other medications that the investigator deems to be medically necessary.

The Exclusion Criteria describes other medications which are prohibited in this trial.

There are no prohibited therapies during the Post-Treatment Follow-up Phase.

## 4.6 Rescue Medications & Supportive Care

### 4.6.1 Supportive Care Guidelines

Subjects should receive appropriate supportive care measures as deemed necessary by the treating investigator. Suggested supportive care measures for the management of adverse events with potential immunologic etiology are outlined below and in greater detail in the ECI guidance document. Where appropriate, these guidelines include the use of oral or intravenous treatment with corticosteroids as well as additional anti-inflammatory agents if symptoms do not improve with administration of corticosteroids. Note that several courses of steroid tapering may be necessary as symptoms may worsen when the steroid dose is decreased. For each disorder, attempts should be made to rule out other causes such as metastatic disease or bacterial or viral infection, which might require additional supportive care. The treatment guidelines are intended to be applied when the investigator determines the events to be related to pembrolizumab.

Note: if after the evaluation the event is determined not to be related, the investigator is instructed to follow the ECI reporting guidance but does not need to follow the treatment guidance (as outlined in the ECI guidance document). Refer to Section 4.2.1 for dose modification.

It may be necessary to perform conditional procedures such as bronchoscopy, endoscopy, or skin photography as part of evaluation of the event. Suggested conditional procedures, as appropriate, can be found in the ECI guidance document.

- **Pneumonitis:**

- For **Grade 2 events**, treat with systemic corticosteroids. When symptoms improve to Grade 1 or less, steroid taper should be started and continued over no less than 4 weeks.
- For **Grade 3-4 events**, immediately treat with intravenous steroids. Administer additional anti-inflammatory measures, as needed.
- Add prophylactic antibiotics for opportunistic infections in the case of prolonged steroid administration.

- **Diarrhea/Colitis:**

Subjects should be carefully monitored for signs and symptoms of enterocolitis (such as diarrhea, abdominal pain, blood or mucus in stool, with or without fever) and of bowel perforation (such as peritoneal signs and ileus).

- All subjects who experience diarrhea/colitis should be advised to drink liberal quantities of clear fluids. If sufficient oral fluid intake is not feasible, fluid and electrolytes should be substituted via IV infusion. For Grade 2 or higher diarrhea, consider GI consultation and endoscopy to confirm or rule out colitis.
- For **Grade 2 diarrhea/colitis** that persists greater than 3 days, administer oral corticosteroids.
- For **Grade 3 or 4 diarrhea/colitis** that persists > 1 week, treat with intravenous steroids followed by high dose oral steroids.
- When symptoms improve to Grade 1 or less, steroid taper should be started and continued over no less than 4 weeks.

- **Type 1 diabetes mellitus (if new onset, including diabetic ketoacidosis [DKA]) or  $\geq$  Grade 3 Hyperglycemia, if associated with ketosis (ketonuria) or metabolic acidosis (DKA)**
  - For **T1DM** or **Grade 3-4** Hyperglycemia
    - Insulin replacement therapy is recommended for Type I diabetes mellitus and for Grade 3-4 hyperglycemia associated with metabolic acidosis or ketonuria.
    - Evaluate patients with serum glucose and a metabolic panel, urine ketones, glycosylated hemoglobin, and C-peptide.

- **Hypophysitis:**
  - For **Grade 2** events, treat with corticosteroids. When symptoms improve to Grade 1 or less, steroid taper should be started and continued over no less than 4 weeks. Replacement of appropriate hormones may be required as the steroid dose is tapered.
  - For **Grade 3-4** events, treat with an initial dose of IV corticosteroids followed by oral corticosteroids. When symptoms improve to Grade 1 or less, steroid taper should be started and continued over no less than 4 weeks. Replacement of appropriate hormones may be required as the steroid dose is tapered.

- **Hyperthyroidism or Hypothyroidism:**

Thyroid disorders can occur at any time during treatment. Monitor patients for changes in thyroid function (at the start of treatment, periodically during treatment, and as indicated based on clinical evaluation) and for clinical signs and symptoms of thyroid disorders.

  - **Grade 2** hyperthyroidism events (and **Grade 2-4** hypothyroidism):

- In hyperthyroidism, non-selective beta-blockers (e.g. propranolol) are suggested as initial therapy.
- In hypothyroidism, thyroid hormone replacement therapy, with levothyroxine or liothyroinine, is indicated per standard of care.
- **Grade 3-4** hyperthyroidism
  - Treat with an initial dose of IV corticosteroid followed by oral corticosteroids. When symptoms improve to Grade 1 or less, steroid taper should be started and continued over no less than 4 weeks. Replacement of appropriate hormones may be required as the steroid dose is tapered.
- **Hepatic:**
  - For **Grade 2** events, monitor liver function tests more frequently until returned to baseline values (consider weekly).
    - Treat with IV or oral corticosteroids
  - For **Grade 3-4** events, treat with intravenous corticosteroids for 24 to 48 hours.
  - When symptoms improve to Grade 1 or less, a steroid taper should be started and continued over no less than 4 weeks.
- **Renal Failure or Nephritis:**
  - For **Grade 2** events, treat with corticosteroids.
  - For **Grade 3-4** events, treat with systemic corticosteroids.
  - When symptoms improve to Grade 1 or less, steroid taper should be started and continued over no less than 4 weeks.

**Management of Infusion Reactions:** Signs and symptoms usually develop during or shortly after drug infusion and generally resolve completely within 24 hours of completion of infusion.

Table 8 below shows treatment guidelines for subjects who experience an infusion reaction associated with administration of pembrolizumab (MK-3475).

Table 8 Infusion Reaction Treatment Guidelines

NCI CTCAE Grade	Treatment	Premedication at subsequent dosing
Grade 1 Mild reaction; infusion interruption not indicated; intervention not indicated	Increase monitoring of vital signs as medically indicated until the subject is deemed medically stable in the opinion of the investigator.	None
Grade 2 Requires infusion interruption but responds promptly to symptomatic treatment (e.g., antihistamines, NSAIDS, narcotics, IV fluids); prophylactic medications indicated for <=24 hrs	
Stop Infusion and monitor symptoms. Additional appropriate medical therapy may include but is not limited to:
 
 
IV fluids
 
Antihistamines
 
NSAIDS
 
Acetaminophen
 
Narcotics
 
 
Increase monitoring of vital signs as medically indicated until the subject is deemed medically stable in the opinion of the investigator.
 
If symptoms resolve within one hour of stopping drug infusion, the infusion may be restarted at 50% of the original infusion rate (e.g., from 100 mL/hr to 50 mL/hr). Otherwise dosing will be held until symptoms resolve and the subject should be premedicated for the next scheduled dose.
 
Subjects who develop >Grade 2 toxicity despite adequate premedication should be permanently discontinued from further trial treatment administration.
	Subject may be premedicated 1.5h ( $\pm$ 30 minutes) prior to infusion of pembrolizumab (MK-3475) with: Diphenhydramine 50 mg po (or equivalent dose of antihistamine). Acetaminophen 500-1000 mg po (or equivalent dose of antipyretic).
Grades 3 or 4  Grade 3: Prolonged (i.e., not rapidly responsive to symptomatic medication and/or brief interruption of infusion); recurrence of symptoms following initial improvement; hospitalization indicated for other clinical sequelae (e.g., renal impairment, pulmonary infiltrates)  Grade 4: Life-threatening; pressor or ventilatory support indicated	
Stop Infusion. Additional appropriate medical therapy may include but is not limited to:
 
 
IV fluids
 
Antihistamines
 
NSAIDS
 
Acetaminophen
 
Narcotics
 
Oxygen
 
Pressors
 
Corticosteroids
 
Epinephrine
 
 
Increase monitoring of vital signs as medically indicated until the subject is deemed medically stable in the opinion of the investigator.
 
Hospitalization may be indicated.
 
Subject is permanently discontinued from further trial treatment administration.
	No subsequent dosing
Appropriate resuscitation equipment should be available in the room and a physician readily available during the period of drug administration.		

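### The suggested steroid trigger for Grade 3 or 4 diarrhea/colitis (more than 1 week) comes later than the one for Grade 2 (more than 3 days), and no other Grade 3-4 steroid line in Section 4.6.1 has a wait

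*Combined protocol and SAP*

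**What the plan says.** Section 4.6.1 (Supportive Care Guidelines) sets out, organ by organ, how to manage immune-type adverse events that the investigator judges related to pembrolizumab. Section 4.2.1.2 refers the reader to it, and to a separate ECI guidance document, for corticosteroid use.

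Under Diarrhea/Colitis, adjacent bullets give the steroid triggers:

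- Grade 2: disease "that persists greater than 3 days, administer oral corticosteroids".
- Grade 3 or 4: disease "that persists > 1 week, treat with intravenous steroids followed by high dose oral steroids".

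The section describes its content as "Suggested supportive care measures for the management of adverse events with potential immunologic etiology" and leaves supportive care to the treating investigator's judgement.

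**The concern.** One would expect the prompt to treat to come sooner, or at least no later, as severity rises. Here it comes later. Table 11 in Section 6.2.4 makes the ordering harder to defend: it describes Grade 3 as warranting hospitalization and Grade 4 as life-threatening and calling for urgent intervention. The colitis paragraph itself warns of bowel perforation.

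What is at stake is participant safety. An investigator who opens the protocol to manage severe colitis finds a bullet that gives no steroid prompt in the first week. The bullet above it would already have prompted steroids, after 3 days, in a patient with milder disease.

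**Working it through.** No power, sample size or error rate is involved, so the check is a side-by-side reading of every steroid line in Section 4.6.1.

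**Step 1: the two colitis triggers**

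| Grade | Written trigger | Treatment |
|---|---|---|
| 2 | more than 3 days | oral corticosteroids |
| 3 or 4 | more than 1 week (7 days) | intravenous, then high-dose oral |

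Difference: 7 − 3 = 4 days later at the higher grade. Between the two triggers, on days 4 to 7, a Grade 2 case meets a steroid line and a Grade 3 or 4 case does not.

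**Step 2: the other Grade 3-4 steroid lines**

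| Event | Instruction | Waiting period |
|---|---|---|
| Pneumonitis | "immediately treat with intravenous steroids" | none |
| Hypophysitis | "treat with an initial dose of IV corticosteroids followed by oral corticosteroids" | none |
| Hyperthyroidism | "Treat with an initial dose of IV corticosteroid followed by oral corticosteroids" | none |
| Hepatic | "treat with intravenous corticosteroids for 24 to 48 hours" | none (the hours are a treatment duration) |
| Renal failure or nephritis | "events, treat with systemic corticosteroids" | none |

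Of the six Grade 3-4 lines that direct steroid treatment, only colitis has a wait (0 of the other 5). Table 8, in the same section, also lists corticosteroids as one option for Grade 3 or 4 infusion reactions, again with no wait. Counting it makes the comparison 0 of 6 and changes nothing.

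**Step 3: the Grade 2 steroid lines**

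Pneumonitis, hypophysitis, hepatic and renal events have no wait at Grade 2; colitis has more than 3 days. Colitis is thus the only one of five with a wait at this grade too. Having some wait is a consistent feature of the colitis guidance. Having a longer one at the higher grade is the anomaly.

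**Step 4: is an earlier start set elsewhere?**

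- Table 3a (Section 4.2.1.2) holds pembrolizumab for Grade 2-3 diarrhea/colitis and stops it permanently at Grade 4. It mentions tapering steroids but gives no time for starting them.
- Section 4.5.2 exempts suspected immune events from the ban on systemic steroids. That is permission, not a prompt.
- Table 11 (Section 6.2.4) defines the grades but does not mention steroids.

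None of these sets an earlier steroid start for Grade 3 or 4 colitis.

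**The case against.** The strongest reply is that the text is advisory and incomplete by design. The measures are suggestions, steroids are allowed at any time for a suspected immune event, and pembrolizumab is held or stopped regardless. A physician who has graded colitis as 3 or 4 already has a strong signal to act. The fuller instructions are in the ECI guidance document, which may well set an earlier start. This stands as a limit: the consequence at the bedside cannot be established from the protocol, and passive waiting for a week is an unlikely way for a physician to act. It does not repair the protocol's own wording, to which Section 4.2.1.2 directs the reader.

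A second reply is that diarrhea differs from the other events because infection must be excluded and endoscopy may be needed first. That could explain having a wait. It does not explain a longer one for sicker patients, and ruling out other causes is required for every disorder in the section.

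A third is that the two bullets compare different treatments and may describe escalation: oral steroids after 3 days, intravenous after a week. That reading is possible, but the oral-steroid bullet is limited to Grade 2 and no escalation is stated. If that is the intent, the wording still needs to change.

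Finally, the protocol alone does not show whether immediate treatment or the 3-day trigger is clinically right for Grade 3 or 4. That is a fair point, and the fix leaves the exact timing to the clinical team.

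**Conclusion.** The concern holds. As written, the steroid trigger for diarrhea/colitis is inverted by grade: more than 3 days at Grade 2 and more than 7 days at Grade 3 or 4, a difference of 4 days in the wrong direction. No other Grade 3-4 steroid line in Section 4.6.1 has a waiting period, and no section checked sets an earlier start. The conclusion rests on a literal reading of the protocol and assumes nothing about the ECI guidance document. It is a safety-guidance defect that should be corrected; it does not impose a delay, and it has no bearing on sample size, endpoint or analysis.

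**What to change.** Amend the Grade 3 or 4 bullet by deleting the persistence condition, for example: *For Grade 3 or 4 diarrhea/colitis, start intravenous steroids, then change to high-dose oral steroids.* This gives it the same unconditional form as the other five Grade 3-4 lines. At minimum, state that steroids for Grade 3 or 4 begin no later than the Grade 2 trigger of more than 3 days, which removes the inversion. If stepwise escalation was intended, write it out.

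Before the amendment is finalised, the clinical team should check the timing against the ECI guidance document so that the two agree. The cost is a one-line wording change, with no effect on visits, sample size or analysis.
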